21. Body surface area (BSA)-adjusted creatinine clearance <50 mL/min/1.73 m² at Screening (Visit 1), calculated using the Cockcroft-Gault equation: [(140 - age) × mass (kg) × [0.85 if female] / 72 × serum creatinine (mg/dL) × BSA (m²)/1.73]. Repeat testing is allowed once, if clinically appropriate
22. Alcohol and/or drug abuse within 6 months prior to Screening (Visit 1), as defined by Diagnostic and Statistical Manual – Fifth Edition Text Revision Criteria for Substance Abuse
23. Female patients who are pregnant or breastfeeding
24. Sexually active female patients, who are not surgically sterile or at least 2 years postmenopausal prior to Screening (Visit 1), and do not agree to utilize a highly effective hormonal method of contraception (an intrauterine device or vasectomized male partner is also acceptable), in combination with a barrier method, from Screening (Visit 1) through at least 4 weeks after the completion of study treatment
25. Male patients not using highly effective contraception or not agreeing to continue highly effective contraception through at least 90 days after the completion of study treatment
26. Known allergy to any ingredients of the study treatment or placebo (pridopidine, silicified microcrystalline cellulose, magnesium stearate)
27. Treatment with any investigational product within 30 days of Screening (Visit 1) or patients planning to participate in another clinical study assessing any investigational product during the study
28. Planned elective surgery during study participation

Study Design:

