 - (ii) history of complex arrhythmia (multifocal premature ventricular contractions, bigeminy, trigeminy, ventricular tachycardia) that was symptomatic or required treatment (Common Terminology Criteria for Adverse Events grade 3), symptomatic or uncontrolled atrial fibrillation despite treatment, or asymptomatic sustained ventricular tachycardia
 - (iii) symptomatic bradycardia, sick sinus syndrome or atrioventricular block greater than first degree in the absence of a functioning pacemaker
 - (iv) unexplained syncope
 - (v) Brugada syndrome
 - (vi) hypertrophic cardiomyopathy
14. History of congenital long QT syndrome or a first degree relative with this condition
15. History of epilepsy or of seizures within 5 years prior to Baseline (Visit 2)
16. History of clinically significant deficit from stroke or transient ischemic attack within 6 months prior to Screening (Visit 1)
17. Serum potassium, magnesium and/or calcium levels outside of the central laboratory's reference range at Screening (Visit 1) visit and considered clinically significant by the investigator. Repeat testing is allowed (up to a maximum of three tests) if required to establish whether values are within normal range or not clinically significant
18. Use of all oral cannabinoids (including all preparations containing any cannabinoids, prescribed oral medical marijuana and oral cannabidiol) with the exception of topical formulations of cannabidiol, within 28 days prior to Baseline (Visit 2)

19. Use of medications (within the last 6 weeks prior to Baseline [Visit 2]) that have been demonstrated to prolong the QT interval, or any patients who may require such medications during the course of the study such as but not limited to prohibited antipsychotic medications, tricyclic antidepressants and/or Class I antiarrhythmic (see [Table 3](#) and [Section 5.10.1](#))
20. Treatment with apomorphine during the 28 days prior to Screening (Visit 1)
21. Body surface area (BSA)-adjusted creatinine clearance <50 mL/min/1.73 m² at Screening (Visit 1), calculated using the Cockcroft-Gault equation: $[(140 - \text{age}) \times \text{mass} (\text{kg}) \times [0.85 \text{ if female}]] / [72 \times \text{serum creatinine} (\text{mg/dL}) \times \text{BSA} (\text{m}^2)] / 1.73$. Repeat testing is allowed once, if clinically appropriate

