4.2.1 Reasons for Withdrawal/Discontinuation

Patients are free to withdraw from the study at any time and for any reason without prejudice. The investigator also has the right to withdraw a patient from the study if an intercurrent illness or AE occurred, if the patient did not cooperate, or for any reason concerning the health or well-being of the patient. The reasons for patients not completing the study will be recorded.

Among other reasons, a patient may be discontinued from the study treatment or the study if they meet any of the following stopping rules:

QTcF stopping rules

- QTcF >500 msec (based on the mean value from the triplicate ECG measurements)
- QTcF >480 msec with concurrent increase in QTcF >60 msec (Δ QTcF, based on the mean value from the triplicate ECG measurements) from Baseline (Visit 2)
- Patients with QTcF >480 msec or with an increase of QTcF >60 msec from Baseline (Visit 2) will return to the clinic within 48 to 72 hours for repeat evaluation of electrolyte levels and repeat triplicate ECGs to demonstrate reversibility of the effect on QTcF. Decision on discontinuation will be determined by EAC

Creatinine clearance stopping rule

Patients with an adjusted CrCL <50 mL/min/1.73 m² calculated by CrCL * BSA/1.73, where CrCL is calculated using the Cockcroft-Gault equation $[(140 - \text{age}) \times \text{mass (kg)} \times [0.85 \text{ if female}] / 72 \times \text{serum creatinine (mg/dL)}]$ at any time point after Baseline (Visit 2) will be requested to return to the clinic for an unscheduled visit 1 week later to repeat the CrCL test one more time for confirmation. If the repeated CrCL value is confirmed to be <50 mL/min/1.73 m², the patient will be discontinued from the study treatment.

The investigator will also withdraw a patient if Prilenia Therapeutics or regulatory authorities terminate the study. If a patient is discontinued because of an AE, the event will be followed until it has resolved.

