6.8 Clinical Laboratory Analyses/Evaluations

A laboratory test result that has significantly worsened (according to medical judgment) from Visit 2 result will be recorded on the source documentation, transcribed onto the eCRF as an AE, and monitored as described in [Section 6.5.1.4](#).

Clinical laboratory tests will be performed using a central laboratory, as identified in the Laboratory Procedures Manual provided in the study file documents.

The safety laboratory tests will include:

Haematology: white cell count and differential count, red cell count, hemoglobin, hematocrit, mean cell volume, mean cell hemoglobin, mean cell hemoglobin concentration, platelet count.

Clinical Serum Chemistry: calcium, sodium, potassium, magnesium chloride, bicarbonate or carbon dioxide, glucose, blood urea nitrogen (BUN), creatinine, cholesterol, uric acid, total bilirubin, alkaline phosphatase, gamma glutamyl transpeptidase (GGT), alanine aminotransferase, aspartate aminotransferase, total protein, albumin, lactate dehydrogenase, creatinine phosphokinase (in case of elevated creatinine phosphokinase, the muscle/brain [MB] fraction should be measured), direct bilirubin, indirect bilirubin, prolactin. The prolactin should

be blinded to all the clinical staff, Prilenia Therapeutics and/or its designee. In case of a safety concern, the Investigator will be notified by the central laboratory.

Urinalysis: protein, glucose, ketones, blood (hemoglobin), pH, specific gravity, leukocyte esterase, microscopic (bacteria, red blood cells, white blood cells, casts, crystals). A dipstick urine pregnancy test will be performed as noted in the schedule of assessments ([Table 4](#)).

Patients with CrCL <50 mL/min/1.73 m² calculated using the Cockcroft-Gault equation [(140 - age) × mass (kg) × [0.85 if female] / 72 × serum creatinine (mg/dL)] at any time point after Baseline (Visit 2) will be requested to return to the clinic for an unscheduled visit 1 week later to repeat the CrCL test one more time for confirmation. If the repeated CrCL value is confirmed to be <50 mL/min/1.73 m², the patient will be discontinued from the study treatment.

Any decrease in CrCL that is judged by the investigator as a clinically significant change (worsening) from Baseline (Visit 2) result will be considered an AE, recorded on the source documentation, transcribed onto the eCRF, and monitored as described in [Section 6.5.1.4](#).

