## Statistical Analysis Plan

- QTc parameters: absolute QTcF of >450 msec, >480 msec and ≤500 msec, and >500 msec, mean QTcF, changes in QTcF>30 msec and ≤60 msec, and changes in QTcF>60 msec throughout the study.
- Clinical safety laboratory (Only Creatinine Clearance, Serum Creatinine, Potassium and Magnesium), vital signs (including assessment of orthostatic hypotension), physical and neurological examination, concomitant medications throughout the study.
- Columbia-Suicide Severity Rating Scale (C-SSRS)- At baseline and Since last visit throughout the study.
- Change from Baseline (Visit 2) in impulse control disorder as evaluated by the Questionnaire for Impulsive Compulsive Disorders in Parkinson's Disease Rating Scale (QUIP-RS) throughout the study.
- Tolerability
  - The number (%) of subjects who complete the study drug
  - The number (%) of subjects who fail to complete the study drug due to AEs
  - The number (%) of subjects who fail to complete the study drug due to QTcF and QT stopping rules, seizure or convulsions.

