### 15.4 Laboratory Safety Parameters

Only select clinical laboratory safety parameters will be converted to consistent units according to the International System of Units (SI) before summarization.

As of development of this SAP only Creatinine Clearance and Serum Creatinine will be summarized as below. Any other available data will be included in listings.

The following will be summarized:

- Numeric laboratory parameters: In case the value of a numeric laboratory parameter is below the lower limit of quantification, the lower limit of quantification will be used as the response value for the purpose of calculating the descriptive statistics.
- Laboratory parameters which have an upper and/or lower reference range: Number and percentage of subjects with 6 categories (missing, clinically significant low, not clinically significant low, normal, not clinically significant high, clinically significant high) values at each visit for each parameter will be summarized by treatment group. If a subject has both low and high abnormalities at a given visit, then only the worst value would be displayed in the appropriate category.
- These values will be presented as a shift table, i.e. the distribution of the 6 response categories at each post-baseline visit and the worst post-baseline value across all visits will be classified by the baseline category.

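### The creatinine-clearance stopping rule is given by two different formulas against one limit, and the body-surface factor in Protocol 4.2.1 is upside down for its own unit

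*Protocol*

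**What the plan says.** Protocol 4.2.1 applies a limit of 50 mL/min/1.73 m² after Baseline to an adjusted creatinine clearance "calculated by CrCL * BSA/1.73, where CrCL is calculated using the Cockcroft-Gault equation".

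Protocol 6.8 restates the rule as "Patients with CrCL <50 mL/min/1.73 m² calculated using the Cockcroft-Gault equation". It then writes out the full equation, with no BSA term and no reference back to 4.2.1. Both sections ask for a repeat test one week later, and both make the stop mandatory: "If the repeated CrCL value is confirmed to be <50 mL/min/1.73 m², the patient will be discontinued from the study treatment". Neither says which formula governs.

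Exclusion criterion 21 uses the same limit at entry: "Body surface area (BSA)-adjusted creatinine clearance <50 mL/min/1.73 m² at Screening (Visit 1), calculated using the Cockcroft-Gault equation". The synopsis prints the end of that formula as "72 × serum creatinine (mg/dL) × BSA (m²)/1.73", and Section 4.1.2 brackets it differently.

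The SAP keeps creatinine clearance among a short list of laboratory endpoints in Section 6.4 ("Clinical safety laboratory (Only Creatinine Clearance, Serum Creatinine, Potassium and Magnesium"). In Section 15.4 it narrows the list further: "only Creatinine Clearance and Serum Creatinine will be summarized". It gives no formula for creatinine clearance.

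**The concern.** There are two separate defects.

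- **Two formulas for one decision.** A site or programmer working from 4.2.1 and one working from 6.8 can reach opposite decisions for the same patient on the same day.
- **An inverted factor.** Multiplying mL/min by BSA/1.73 does not give mL/min per 1.73 m². It moves the result away from the normalised value, so large patients look better than they are and small patients look worse.

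The rule protects patients with reduced renal function. If it fires late, a large patient stays on drug below the stated limit. If it fires early, a small patient loses treatment without cause. The confirmatory repeat does not help, because it applies the same formula.

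Exclusion criterion 21 may add a third problem. Its bracketing is ambiguous, and I do not claim that it is inverted. If it is meant to divide by BSA/1.73, which is the unit-consistent form, then the entry rule and the 4.2.1 stopping rule adjust for body size in opposite directions.

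**Working it through.** **Inputs.** The limit of 50 mL/min/1.73 m² and the two formulas come from Protocol 4.2.1 and 6.8. The documents give no BSA or clearance distribution, so the BSA values and example patients below are assumptions. BSA for the examples is by the Mosteller formula, sqrt(cm × kg / 3600).

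**Formulas.** Let C be raw Cockcroft-Gault in mL/min: C = (140 − age) × kg × (0.85 if female) / (72 × serum creatinine).

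- 4.2.1 fires when C × BSA/1.73 < 50, so when C < 50 × 1.73/BSA.
- 6.8 fires when C < 50.
- The unit-consistent rule fires when C × 1.73/BSA < 50, so when C < 50 × BSA/1.73.

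**Raw C (mL/min) below which each rule fires**

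| BSA (m²) | 4.2.1 | 6.8 | Unit-consistent | Normalised clearance at the 4.2.1 trigger, 50 × (1.73/BSA)² |
|---|---|---|---|---|
| 1.5 | 57.7 | 50 | 43.4 | 66.5 |
| 1.73 | 50.0 | 50 | 50.0 | 50.0 |
| 1.9 | 45.5 | 50 | 54.9 | 41.5 |
| 2.0 | 43.2 | 50 | 57.8 | 37.4 |
| 2.2 | 39.3 | 50 | 63.6 | 30.9 |

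The last column shows what the nominal limit of 50 means under 4.2.1: it runs from 66.5 at BSA 1.5 to 30.9 at BSA 2.2.

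**Serum creatinine (mg/dL) above which each rule fires.** With k = (140 − age) × kg × (0.85 if female)/72, the triggers are k × (BSA/1.73)/50 for 4.2.1, k/50 for 6.8 and k × (1.73/BSA)/50 for the unit-consistent rule.

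- Man, 70 y, 85 kg, 175 cm: k = 70 × 85/72 = 82.64, BSA 2.03. Triggers: 1.94 / 1.65 / 1.41.
- Woman, 70 y, 50 kg, 155 cm: k = 70 × 50 × 0.85/72 = 41.32, BSA 1.47. Triggers: 0.70 / 0.83 / 0.97.

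With Du Bois BSA the man's triggers are 1.92 / 1.65 / 1.43 and the woman's are unchanged, so the choice of BSA formula matters little.

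**Decisions for single patients**

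- The same woman at creatinine 0.75: C = 2975/54 = 55.1. Under 4.2.1 the value is 46.7 (stop); under 6.8 it is 55.1 (continue); unit-consistent it is 65.0 (continue).
- Man, 70 y, 100 kg, 183 cm, creatinine 1.7, BSA 2.25: C = 7000/122.4 = 57.2. Under 4.2.1 the value is 74.5 and under 6.8 it is 57.2 (both continue); unit-consistent it is 43.9 (stop).

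**Only if exclusion criterion 21 divides by BSA/1.73.** Entry then needs C of at least 50 × BSA/1.73, and the 4.2.1 trigger is (1.73/BSA)² times that entry minimum.

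- BSA 1.5: the ratio is 1.330. A patient with C between 43.4 and 57.7 is eligible, and would be below the 4.2.1 limit at the first post-baseline test with no change in renal function.
- BSA 1.9: the ratio is 0.829. A patient at the entry minimum must lose 17% of raw clearance before 4.2.1 fires.
- BSA 2.2: the ratio is 0.618. The required loss is 38% (63.6 to 39.3).

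**The case against.** The mismatch looks like an editing lag. The summary of changes lists 4.2.1 among the sections updated in version 2.0 and does not list 6.8, and it says the renal exclusion criterion was moved to a BSA adjustment. So the intended rule is probably the adjusted one, and 6.8 is probably old text. That explains the mismatch, but both sections are current protocol text with no order of precedence, and reading 6.8 as shorthand for 4.2.1 leaves the inversion in place.

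Other safeguards exist. The investigator may withdraw a patient on health grounds, and a clinically significant fall in clearance is an adverse event. These soften the late stop in a large patient. They do not prevent the premature stop in a small one.

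The inverted formula may never have been used. The protocol says "Clinical laboratory tests will be performed using a central laboratory", and the documents do not say who computes clearance or with what programmed formula. This stands as a limit on what can be concluded about conduct.

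The remaining use is limited. The SAP was written after the decision to terminate, Section 9.3 says termination came before 30 subjects were enrolled, and the categories in 15.4 rest on reference ranges and clinical significance, not on the limit of 50. This also stands, and it keeps the point below a critical one. It does not remove it, because the SAP still summarises creatinine clearance and leaves the programmer to choose among conflicting protocol formulas.

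The exclusion criterion 21 figures depend on one reading of ambiguous brackets. They are given as conditional, and the conclusion does not rest on them.

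**Conclusion.** The concern holds on both counts. Protocol 4.2.1 and 6.8 give different formulas for the same mandatory stop, and they agree only at BSA 1.73 m². The 4.2.1 factor adjusts in the wrong direction for its printed unit, by (1.73/BSA)² relative to the unit-consistent trigger: 1.33 times at BSA 1.5 and 0.62 times at BSA 2.2. The 6.8 version has no adjustment and so does not match its unit either.

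The algebra needs no assumption beyond the printed formulas and the unit. The example patients and BSA values are assumed. The number of subjects affected cannot be estimated from the documents. It is likely to be small, because enrolment stopped below 30 and only patients near the limit can be reclassified. This should be fixed, as a safety threshold that is wrong as written. It does not bear on the efficacy analysis plan.

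**What to change.** Use one formula throughout: {[(140 − age) × kg × (0.85 if female)] / [72 × serum creatinine]} × 1.73/BSA, compared with 50 mL/min/1.73 m².

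- Put it in Protocol 4.2.1 and 6.8, and bracket exclusion criterion 21 to match in both the synopsis and 4.1.2.
- State the same derivation in SAP 15.4 and name the BSA formula.
- Add a listing of any subject whose on-study value falls on a different side of 50 under the corrected formula than under the one applied, and record which formula that was.

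The cost is low: one derivation line and one listing in the SAP, which was still to be finalised before database lock, plus a protocol clarification. No new data are needed. Weight is taken at every clinic visit and height at Screening (Protocol 6.5.3), and serum creatinine is in the chemistry panel (Protocol 6.8).

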4.2.2 Handling of Withdrawals

The reason(s) for withdrawal will be documented in the patient's electronic case report form (eCRF). Patients withdrawing from the study will be encouraged to complete the same final evaluations as patients completing the study according to this protocol, particularly safety evaluations. The aim is to record data in the same way as for patients who completed the study. Reasonable efforts will be made to contact patients who are lost to follow-up. These efforts

must be documented in the patient's file. The sponsor has the right to terminate the study at any time in case of serious AEs (SAEs) or if special circumstances concerning the study treatment or the company itself occur, making further treatment of patients impossible. In this event, the investigator(s) will be informed of the reason for study termination.

4.2.3 Replacements

Patients who withdraw, are withdrawn by the investigator, or are lost to follow-up after randomization will not be replaced.

5 Study Treatments

The study treatment will be oral capsules containing 75 mg and 100 mg of pridopidine and matching placebo capsules (as the control treatment product) identical in appearance.

Pridopidine capsules contain the active ingredient pridopidine (75 mg or 100 mg) and inactive excipients. The excipients are [REDACTED].

The investigational product will be produced and packed in 60 count bottles provided by [REDACTED]

The secondary packaging and labeling of study treatment will be performed by [REDACTED]. All packaging and labeling operations for study treatment will be performed according to Good Manufacturing Practice for Medicinal Products and the relevant regulatory requirements.

Bottles containing the investigational product or placebo capsules will be packed in kits. Each medication kit will contain two distinct labeled bottles in accordance with the associated treatment arm. Both outer pack and bottles will be labeled with a unique pack number.

Four types of kit will be prepared for use in this study:

- Kit type 1: One bottle of 75 mg pridopidine and one bottle of placebo
- Kit type 2: One bottle of 100 mg pridopidine and one bottle of placebo
- Kit type 3: Two bottles of 75 mg pridopidine
- Kit type 4: Two bottles of placebo

5.1 Method of Assigning Patients to Treatment Groups

Patients will be randomly assigned at Baseline (Visit 2) to receive pridopidine 100 mg BID, 150 mg BID or placebo using a 1:1:1 allocation ratio.

An interactive web response system (IWRS) will be used to administer the randomization schedule. Biostatistics will generate the randomization schedule using SAS software Version 9.4 or later (SAS Institute Inc, Cary, North Carolina) for IWRS, which will link sequential patient randomization numbers to treatment codes.

5.2 Treatments Administered

Study treatments and matching placebo will be administered as oral capsules. During the 16-week active treatment period, the first study treatment daily dose will be taken between 6:00 and 8:00 AM and the second study treatment daily dose will be taken 6 to 10 hours after

the first study treatment dose administration and not later than 5:00 PM. The second study treatment daily dose should be taken 0 to 120 minutes BEFORE the “scheduled levodopa dose” (NOT after). As much as possible, study treatment should be taken at the same time throughout the study.

Capsules will be swallowed whole with water. Study treatment can be taken irrespective of meals.

If a patient misses a study treatment dose(s) on a non-clinic day, the following guidelines should be followed:

- If the first study daily treatment dose is missed, it can be taken up to 11:00 AM that day. If it is not taken by 11:00 AM, the first study daily treatment dose should be skipped, and the patient continues to the normal dosing schedule
- If the second study daily treatment dose is missed, it can be taken up to 5:00 PM that day. If it is not taken by 5:00 PM, the second study daily treatment dose should be skipped, and the patient continues to the normal dosing schedule the following day

If a patient misses the morning study treatment dose on an in-clinic day, the visit should be re-scheduled.

Patients randomized to each of the active treatment arms, **pridopidine 100 mg BID or 150 mg BID** will receive the following during these designated periods in the study (as per the schedule detailed in [Section 5.4.1](#)):

1. Up-titration-period (Weeks 1 through 4)
 - a. Week 1-3: One kit type 1 (one bottle of 75 mg pridopidine capsules and one bottle of placebo capsules in a blinded fashion):
 - i. Week 1 (Days 1-7) - patients will receive one capsule of study medication from each of the 2 bottles, every other day (Q48h) (either AM or PM).
 - ii. Week 2 (Days 8-14) - patients will receive one capsule of study medication from each of the 2 bottles, once per day (QD) (either AM or PM). The total daily dose will be 75 mg pridopidine.
 - iii. Week 3 (Days 15-21)- patients will receive one capsule of study medication from each of the 2 bottles, twice per day (BID). The total daily dose will be 150 mg pridopidine.
 - b. Week 4: One kit type 2 (one bottle of 100 mg pridopidine and one bottle of placebo in a blinded fashion):

- i. Week 4 (Days 22-28) - patients will receive one capsule of study medication from each of the 2 bottles, BID. The total daily dose will be 200 mg pridopidine.
2. Maintenance period (Weeks 5 to 16) -
 - a. **100 mg BID arm**, patients will receive 3 kits type 2 (each comprises one bottle of 100 mg pridopidine capsules and one bottle of placebo capsules in a blinded fashion), in total 3 kits for 12 weeks.
 - i. Weeks 5 -16 (Days 29 to 112) - patients will receive one capsule of 100 mg pridopidine and one capsule of placebo, one capsule from each of the 2 bottles, BID (total daily dose of 200 mg pridopidine). On Day 1 of Week 5 (Day 29), the first daily dose patients will take before coming to Visit 3 is from the up-titration kit they used during Week 4.
 - b. **150 mg BID arm**, patients will receive 3 kits type 3 (each comprises 2 bottles of 75 mg pridopidine capsules in a blinded fashion), in total 3 kits for 12 weeks.
 - i. Weeks 5-16 (Days 29 to 112) - patients will receive 2 capsules of 75 mg pridopidine, one capsule from each of the 2 bottles, BID (total daily dose of 300 mg pridopidine).
3. Down-titration period (Week 17)-
 - a. Patients will receive one kit type 1 (one bottle of 75 mg pridopidine capsules and one bottle of placebo capsules in blinded fashion):
 - i. Week 17 (Days 1 to 2) - patients will receive one capsule of study medication from each of the 2 bottles, BID. The total daily dose will be 150 mg pridopidine.
 - ii. Week 17 (Days 3 to 4) - patients will receive one capsule of study medication from each of the 2 bottles, QD (either AM or PM). The total daily dose will be 75 mg pridopidine.

Patients randomized to the **placebo treatment arm** will receive the following during these designated periods in the study (as per schedule detailed in [Section 5.4.1](#)):

1. Up-titration period (Weeks 1 through 4)

a. Weeks 1 – 3: One kit type 4 (two bottles of placebo in blinded fashion):

- i) Week 1 (Days 1-7) - patients will receive 2 capsules of placebo (one capsule from each of the 2 bottles), every other day (Q48h) (either AM or PM).
- ii) Week 2 (Days 8-14) - patients will receive 2 capsules of placebo (one capsule from each of the 2 bottles), once per day (QD) (either AM or PM).
- iii) Week 3 (Days 15-21) - patients will receive 2 capsules of placebo (one capsule from each of the 2 bottles), twice per day (BID).

b. Week 4: One kit type 4 (two bottles of placebo in blinded fashion):

- i) Week 4 (Days 22-28) - patients will receive 2 capsules of placebo (one capsule from each of the 2 bottles), twice per day (BID).

2. Maintenance period (Weeks 5 to 16) –

a. Patients will receive 3 kits type 4 (each comprises 2 bottles of placebo), in total 3 kits for 12 weeks.

- i) Week 5-16 (Days 29 to 112) - patients will receive 2 capsules of placebo (one capsule from each of the 2 bottles), BID. On Day 1 of Week 5 (Day 29), the first daily dose patients will take before coming to Visit 3 is from the up-titration kit they used during Week 4.

3. Down-titration period (Week 17):

a. Patients will receive one kit type 4 (two bottles of placebo in blinded fashion):

- i. Week 17 (Days 1 to 2) - patients will receive two capsules of placebo (one capsule from each of the two bottles), BID.
- ii. Week 17 (Days 3 to 4) - patients will receive 2 capsules of study medication (one capsule from each of the 2 bottles), QD (either AM or PM).

